Appendix 2.2.4. Liver Function Tests

Alanine aminotransferase (ALT), aspartate aminotransferase (AST), alkaline phosphatase (ALKP), gamma-glutamyl transferase (GGT), and total bilirubin (TBILI) samples will be taken according to the Schedule of Activities given in the protocol.

CCI [Redacted]

Table A2.2-7: Summary Statistics for ALT, AST, ALKP, GGT, and TBILI Over Time

Weeks	Parameters	Summary Statistics
Baseline, 2, 4, 6, 8, 12, 16, FU	ALT, AST, ALKP, GGT, TBILI in “diagnosed/presumed nonalcoholic steatohepatitis subjects”	N, arithmetic mean, median, %CV, standard deviation, minimum, maximum, Q1, Q3

CCI [Redacted]

Note: FU = 1st Follow-up as defined in Tables 1 and 2 of the protocol

Derived Parameters

Individual percent change from baseline and relative change from baseline over time for each liver function test concentration will be calculated. CCI [Redacted]

[Redacted] percent change from baseline will be summarized by randomized arm, and week as follow:

Table A2.2-8: Summary Statistics for Percent Change From Baseline in Liver Function Test (ALT, AST, ALKP, GGT, and TBILI) Concentrations Over Time

Weeks	Parameter	Population	Summary Statistics
Baseline, 2, 4, 6, 8, 12, 16, FU	Percent Change from baseline for each liver function test (ie ALT, AST, ALKP, GGT, TBILI)	Subjects with “diagnosed / presumed nonalcoholic steatohepatitis”	N, arithmetic mean, median, standard deviation, minimum, maximum, Q1, Q3

CCI [Redacted]

Note: FU = 1st Follow-up as defined in Tables 1 and 2 of the protocol

Figure (1 set for each liver function test parameter CCI [Redacted]):

[Redacted]

- Median response versus week will be presented against randomized arm. Q1 and Q3 values will be added.
- Median percent change from baseline versus week will be presented against randomized arm. A reference line cutting the Y-Axis at 0 will be overlaid. Q1 and Q3 values will be added.

Additional Figure for ALT concentrations only in Subjects with “diagnosed / presumed nonalcoholic steatohepatitis”

- Box and whisker plots for individual percent change from baseline at week 16 versus total daily dose will be presented and overlaid with arithmetic means. Only box, whiskers, median, arithmetic mean and outliers should be reported in this graphic. Total daily dose will be considered as categorical (see Appendix 3.1).

CCI

CCI

CCI

Appendix 2.2.6. Lipid Panel

All lipids will be assessed on the fasting state using serum matrix. Triglycerides(TG), direct low density lipoprotein (LDL-C), very low-density lipoprotein (VLDL), high-density lipoprotein (HDL-C), and total cholesterol samples in subjects with nonalcoholic fatty liver disease (ie entire study population) will be taken according to the Schedule of Activities given in the protocol in subjects with nonalcoholic fatty liver disease.

TG, direct LDL-C, VLDL, HDL-C, and total cholesterol will be listed and summarized by randomized arm, and week as described in Table A2.2-12.

Table A2.2-12: Summary Statistics for TG, Direct LDL-C, HDL-C and Total Cholesterol Over Time

Weeks	Parameters	Summary Statistics
Baseline, 2, 4, 6, 8, 12, 16, FU	TG, direct LDL-C, VLDL, HDL-C, Total Cholesterol	N, arithmetic mean, median, %CV, standard deviation, minimum, maximum, Q1, Q3

Note: FU = 1st Follow-up as defined in Tables 1 and 2 of the protocol

Derived Parameters

For each lipid parameter, individual relative change and percent change from baseline over time will be calculated. Percent change from baseline will be summarized by randomized arm, and week as follow:

Table A2.2-13: Summary Statistics for Percent Change From Baseline in Lipids (ie TG, direct LDL-C, VLDL, HDL-C, and Total Cholesterol) Over Time

Weeks	Derived parameter	Summary Statistics
Baseline, 2, 4, 6, 8, 12, 16, FU	Percent Change from Baseline for each lipid parameter	N, arithmetic mean, median, standard deviation, minimum, maximum, Q1, Q3

Note: FU = 1st Follow-up as defined in Tables 1 and 2 of the protocol

Figure (1 set for each lipid parameter):

- Median response versus week will be presented against randomized arm. Q1 and Q3 values will be added.
- Median percent change from baseline versus week will be presented against randomized arm. A reference line cutting the Y-Axis at 0 will be overlaid. Q1 and Q3 values will be added.

Box and whisker plots by randomized arm and by week will also be displayed to characterize the distribution of percent changes from baseline over time (see Appendix 3.2). Only box, whiskers, arithmetic mean, and outliers should be reported in this graphic.

Figure for triglycerides only (should be included in the safety set of figures)

- For subjects with any **after** Day 1 (ie post-randomization) where fasting TG \geq 600 mg/dL and up to Week 16 (**include** unplanned in chronological/continuous order – not categorical), graph **fasting** TG, FPI, ApoC3, and FPG data together. To do so, real date reported in eCRFe-data loads received from Covance will be used
- If possible, this figure containing 4x4 panels (1 panel per subject) by treatment will be created with LEFT Y-axis reporting TG and FPG levels and RIGHT Y-axis reporting FPI and ApoC3 levels.

Appendix 2.2.7. Glycated Hemoglobin

Glycated hemoglobin (HbA1c) values will be assessed at timepoints described in the Schedule of Activity of the protocol.

HbA1c values will be listed and summarized by randomized arm, and week as described in Table A2.2-14

Table A2.2-14: Summary Statistics for HbA1c Over Time

Weeks	Parameter	Population	Summary Statistics
Baseline, 2, 4, 6, 8, 12, 16, FU	HbA1c	Subjects with nonalcoholic fatty liver disease (ie entire study population)	N, arithmetic mean, median, %CV, standard deviation, minimum, maximum, Q1, Q3
Baseline, 2, 4, 6, 8, 12, 16, FU	HbA1c	T2DM subjects	N, arithmetic mean, median, %CV, standard deviation, minimum, maximum, Q1, Q3

Note: FU = 1st Follow-up as defined in Tables 1 and 2 of the protocol

Derived Parameter

Individual change from baseline over time on HbA1c will be calculated, listed, and summarized by randomized arm, and week as described in Table A2.2-15.

Table A2.2-15: Summary Statistics for Change From Baseline in HbA1c Over Time

Weeks	Derived parameter	Population	Summary Statistics
Baseline, 2, 4, 6,	Change from Baseline	Subjects with nonalcoholic fatty liver disease (ie entire	N, arithmetic mean, median, standard deviation,

Weeks	Derived parameter	Population	Summary Statistics
8, 12, 16, FU		randomized study population)	minimum, maximum, Q1, Q3
2, 4, 6, 8, 12, 16, FU	Change from Baseline	T2DM Randomized Subjects	N, arithmetic mean, median, standard deviation, minimum, maximum, Q1, Q3

[figure not shown]
Note: FU = 1st Follow-up as defined in Tables 1 and 2 of the protocol

Figure (1 set for entire randomized study population and 1 set for T2DM subjects):

- Median response versus week will be presented against randomized arm. Q1 and Q3 values will be added.
- Median change from baseline versus week will be presented against randomized arm. A reference line cutting the Y-Axis at 0 will be overlaid. Q1 and Q3 values will be added.

CCI

Appendix 2.2.9. Fasting Plasma Glucose and Fasting Plasma Insulin (T2DM Subjects Only)

Fasting plasma glucose (FPG) and fasting plasma insulin (FPI) values will be assessed at timepoints described in the Schedule of Activity of the protocol. FPG and FPI values will be listed and summarized by randomized arm, and week as described in Table A2.2-18.

Table A2.2-18: Summary Statistics for FPG And FPI Over Time

Weeks	Parameter	Summary Statistics
Baseline, 2, 4, 6, 8, 12, 16, FU	FPG in subject with T2DM only	N, arithmetic mean, median, %CV, standard deviation, minimum, maximum, Q1, Q3
Baseline, 2, 4, 6, 8, 12, 16	FPI in subject with T2DM only	N, arithmetic mean, median, %CV, standard deviation, minimum, maximum, Q1, Q3

Note: FU = 1st Follow-up as defined in Tables 1 and 2 of the protocol

Note: if plasma glucose concentrations are reported in mmol/L, transform the value in mg/dL using the following equation $Glucose_{(mg/dL)} = 18 * Glucose_{(mmol/L)}$

Derived Parameters

Individual change from baseline over time on FPG and FPI will be calculated, and listed. Changes from baseline will be summarized by randomized arm, and week as described in Table A2.2-19.

Table A2.2-19: Summary Statistics for Change From Baseline in Fasting Plasma Glucose and Fasting Plasma Insulin Over Time

Weeks	Derived parameter	Summary Statistics
2, 4, 6, 8, 12, 16, FU	FPG - change from baseline in subject with T2DM only	N, arithmetic mean, median, standard deviation, minimum, maximum, Q1, Q3
2, 4, 6, 8, 12, 16	FPI - change from baseline in subject with T2DM only	N, arithmetic mean, median, standard deviation, minimum, maximum, Q1, Q3

Note: FU = 1st Follow-up as defined in Tables 1 and 2 of the protocol

Figure (1 set for each parameter):

- Median response versus week will be presented against randomized arm. Q1 and Q3 values will be added.
- Median change from baseline versus week will be presented against randomized arm. A reference line cutting the Y-Axis at 0 will be overlaid. Q1 and Q3 values will be added.

Appendix 2.2.10. Homeostatic Model Assessment for Insulin Resistance (T2DM Subjects Only)

The Homeostatic Model Assessment for Insulin Resistance (HOMA-IR) will be derived using fasting plasma glucose values and fasting plasma insulin values at timepoints described in the Schedule of Activity of the protocol.

The formula used to derive HOMA-IR is as follow:

$$\text{HOMA-IR} = (\text{Glucose}_{\text{Fasting Concentration}} \times \text{Insulin}_{\text{Fasting Concentration}}) / 405$$

where plasma glucose concentrations is reported in mg/dL and plasma insulin is reported in mU/L. As such, HOMA-IR is unit-less.

HOMA-IR values will be listed and summarized by randomized arm, and week as described in Table A2.2-20.

Table A2.2-20: Summary Statistics for HOMA-IR Over Time

Weeks	Parameter	Summary Statistics
Baseline, 2, 4, 6, 8, 12, 16	HOMA-IR in subjects with T2DM only	N, arithmetic mean, median, %CV, standard deviation, minimum, maximum, Q1, Q3

Derived Parameters

Individual change from baseline over time on HOMA-IR will be calculated, and listed. Changes from baseline will be summarized by randomized arm, and week as described in Table A2.2-21.

Table A2.2-21: Summary Statistics for Change From Baseline in HOMA-IR Over Time

Weeks	Derived parameter	Summary Statistics
2, 4, 6, 8, 12, 16	Change from Baseline in in subjects with T2DM only	N, arithmetic mean, median, standard deviation, minimum, maximum, Q1, Q3

Figure:

- Median response versus week will be presented against randomized arm. Q1 and Q3 values will be added.
- Median change from baseline versus week will be presented against randomized arm. A reference line cutting the Y-Axis at 0 will be overlaid. Q1 and Q3 values will be added.

CCI

CCI

Appendix 2.2.12. Serum Apolipoprotein

Serum apolipoprotein (ie ApoA1, ApoB, ApoC3 and ApoE) in subjects with nonalcoholic fatty liver disease (ie entire study population) will be assessed at timepoints described in the Schedule of Activity of the protocol

Each serum apolipoprotein will be listed and summarized by randomized arm, and week as described in Table A2.2-24.

Table A2.2-24: Summary Statistics for Serum Apolipoprotein Over Time

Weeks	Parameter	Summary Statistics
Baseline, 2, 4, 6, 8, 12, 16	ApoA1 in subject with nonalcoholic fatty liver disease	N, arithmetic mean, median, %CV, standard deviation, minimum, maximum, Q1, Q3
Baseline, 2, 4, 6, 8, 12, 16	ApoB in subject with nonalcoholic fatty liver disease	N, arithmetic mean, median, %CV, standard deviation, minimum, maximum, Q1, Q3
Baseline, 2, 4, 6, 8, 12, 16	ApoC3 in subject with nonalcoholic fatty liver disease	N, arithmetic mean, median, %CV, standard deviation, minimum, maximum, Q1, Q3
Baseline, 2, 4, 6, 8, 12, 16	ApoE in subject with nonalcoholic fatty liver disease	N, arithmetic mean, median, %CV, standard deviation, minimum, maximum, Q1, Q3

Derived Parameters

For each serum apolipoprotein, individual relative from baseline and percent change from baseline over time will be calculated. Percent change from baseline will be summarized by randomized arm, and week as follow:

Table A2.2-25: Summary Statistics for Percent Change From Baseline in Serum Apolipoprotein Over Time

Weeks	Parameter	Summary Statistics
2, 4, 6, 8, 12, 16	ApoA1 - Percent Change from Baseline in subject with nonalcoholic fatty liver disease	N, arithmetic mean, median, standard deviation, minimum, maximum, Q1, Q3
2, 4, 6, 8, 12, 16	ApoB - Percent Change from Baseline in subject with nonalcoholic fatty liver disease	N, arithmetic mean, median, standard deviation, minimum, maximum, Q1, Q3
2, 4, 6, 8, 12, 16	ApoC3 - Percent Change from Baseline in subject with nonalcoholic fatty liver disease	N, arithmetic mean, median, standard deviation, minimum, maximum, Q1, Q3
2, 4, 6, 8, 12, 16	ApoE - Percent Change from Baseline in subject with nonalcoholic fatty liver disease	N, arithmetic mean, median, standard deviation, minimum, maximum, Q1, Q3

Figure (1 set for each serum apolipoprotein) :

- Median response versus week will be presented against randomized arm. Q1 and Q3 values will be added.
- Median percent change from baseline versus week will be presented against randomized arm. A reference line cutting the Y-Axis at 0 will be overlaid. Q1 and Q3 values will be added.
- Box and whisker plots by randomized arm and by week will also be displayed to characterize the distribution of percent changes from baseline over time (see Appendix 3.2). Only box, whiskers, median, arithmetic mean, and outliers should be reported in this graphic.

CCI

Appendix 2.2.14. Markers of Apoptotic Activity - CK18-M30 and CK18-M65

Markers of apoptotic activity will be assessed at timepoints described in the Schedule of Activity of the protocol using two circulating biomarkers measuring either the caspase-cleaved cytokeratin-18-M30 (ie CK18-M30) produced during apoptosis or the caspase-cleaved and intact cytokeratin-18-M65 (ie CK18-M65) usually released from cells undergoing necrosis.

CK18-M30 and CK18-M65 levels will be listed and summarized CCI 
 randomized arm, and week as described in Table A2.2-28.

Table A2.2-28: Summary Statistics for CK18-M30 and CK18-M65 Over Time

Weeks	Parameters	Population	Summary Statistics
CCI			

Baseline, 4, 8, 12, 16	CK18-M30	subject with diagnosed/presumed nonalcoholic steatohepatitis	N, arithmetic mean, median, %CV, standard deviation, minimum, maximum, Q1, Q3
Baseline, 4, 8, 12, 16	CK18-M65	subject with diagnosed/presumed nonalcoholic steatohepatitis	N, arithmetic mean, median, %CV, standard deviation, minimum, maximum, Q1, Q3

Derived Parameters

Individual relative change and percent change from baseline over time for each cell death biomarker concentration will be calculated. Percent changes from baseline will be summarized by stratum, randomized arm, and week as follow:

Table A2.2-29: Summary Statistics for Percent Change From Baseline in Cell Death Biomarkers (ie CK18-M30, and CK18-M65) Levels Over Time

Weeks	Parameters	Population	Summary Statistics
CCI			
4, 8, 12, 16	CK18-M30 Percent Change from Baseline	subject with diagnosed/presumed nonalcoholic steatohepatitis	N, arithmetic mean, median, standard deviation, minimum, maximum, Q1, Q3
4, 8, 12, 16	CK18-M65 Percent Change from Baseline	subject with diagnosed/presumed nonalcoholic steatohepatitis	N, arithmetic mean, median, standard deviation, minimum, maximum, Q1, Q3

Figure (1 set for each cell death biomarker CCI):

- Median response versus week will be presented against randomized arm. Q1 and Q3 values will be added.
- Median percent change from baseline versus week will be presented against randomized arm. A reference line cutting the Y-Axis at 0 will be overlaid. Q1 and Q3 values will be added.

Appendix 2.2.15. Collagen formation-related Biomarkers - Pro-C3 and Pro-C6

Collagen formation will be assessed at timepoints described in the Schedule of Activity of the protocol using two circulating biomarkers measuring either N-terminal pro-peptide of type III procollagen (ie Pro-C3) or C-terminal fragment of the α 3 chain of procollagen type VI (ie Pro-C6).

Pro-C3 and Pro-C6 levels will be listed and summarized CCI [redacted] randomized arm, and week as described in Table A2.2-30.

Table A2.2-30: Summary Statistics for Pro-C3 and Pro-C6 Levels Over Time

Weeks	Parameters	Summary Statistics
CCI		
Baseline, 4, 8, 12, 16	Pro-C3 in subjects with diagnosed / presumed nonalcoholic steatohepatitis	N, arithmetic mean, median, %CV, standard deviation, minimum, maximum, Q1, Q3
CCI		
Baseline, 4, 8, 12, 16	Pro-C6 in subjects with diagnosed / presumed nonalcoholic steatohepatitis	N, arithmetic mean, median, %CV, standard deviation, minimum, maximum, Q1, Q3

Derived Parameters

Individual relative change and percent change from baseline over time for each fibrogenesis biomarker will be calculated. Percent changes from baseline will be summarized by stratum, randomized arm, and week as follow:

Table A2.2-31: Summary Statistics for Percent Change From Baseline in Fibrogenesis Biomarkers (ie Pro-C3, and Pro-C6) Levels Over Time

Weeks	Parameters	Population	Summary Statistics
CCI			

4, 8, 12, 16	Pro-C3 Percent Change from Baseline	Subjects with diagnosed / presumed nonalcoholic steatohepatitis	N, arithmetic mean, median, standard deviation, minimum, maximum, Q1, Q3
CCI			
4, 8, 12, 16	Pro-C6 Percent Change from Baseline	Subjects with diagnosed / presumed nonalcoholic steatohepatitis	N, arithmetic mean, median, standard deviation, minimum, maximum, Q1, Q3

Figure (1 set for each fibrogenesis biomarker CCI):

- Median response versus week will be presented against randomized arm. Q1 and Q3 values will be added.
- Median percent change from baseline versus week will be presented against randomized arm. A reference line cutting the Y-Axis at 0 will be overlaid. Q1 and Q3 values will be added.

CCI

CCI

CCI

CCI

CCI

CCI

Appendix 2.3. Data Derivation for Non Standard Safety Endpoints

CCI

CCI

CCI

CCI

CCI

CCI

Appendix 2.4. Compliance

Compliance with double-blinded study medication will be calculated using data entry exclusively from the **oral dosing** CRF pages.

For PPAS determination, compliance will be calculated using ACTIVE bottles only (ie not using all 3 bottles).

The following formula are only indicative when the three bottles are containing active drug and should therefore be adapted for C1171002 study

On Week 4, Week 8, Week 12 and Week 16, the number of tablets used by the subject between each visit will be calculated as below (assuming that each bottle – B1, B2, and B3 - has 38 tablets):

$$\#TabUsed_{Week1-Week4} = (38 - (EndDate - StartDate)_{Week4Page1/3+1}) + (38 - (EndDate - StartDate)_{Week4Page2/3+1}) + (38 - (EndDate - StartDate)_{Week4Page3/3+1})$$

$$\#TabUsed_{Week4-Week8} = (38 - (EndDate - StartDate)_{Week8Page1/3+1}) + (38 - (EndDate - StartDate)_{Week8Page2/3+1}) + (38 - (EndDate - StartDate)_{Week8Page3/3+1})$$

$$\#TabUsed_{Week8-Week12} = (38 - (EndDate - StartDate)_{Week12Page1/3+1}) + (38 - (EndDate - StartDate)_{Week12Page2/3+1}) + (38 - (EndDate - StartDate)_{Week12Page3/3+1})$$

$$\#TabUsed_{Week12-Week16} = (38 - (EndDate - StartDate)_{Week16Page1/3+1}) + (38 - (EndDate - StartDate)_{Week16Page2/3+1}) + (38 - (EndDate - StartDate)_{Week16Page3/3+1})$$

$$\#TabUsed_{DuringStudy} = \#TabUsed_{Week1-Week4} + \#PillsUsed_{Week4-Week8} + \#TabUsed_{Week8-Week12} + \#PillsUsed_{Week12-Week16}$$

Where $\#Tab_{ReturnedBi}$ = Remaining tablets counted in each bottle and reported by site pharmacist in each CRF page as returned amount.

For each subject, the total expected number of tablets used during the study is computed as

$$\#ExpectedTabUsedOverall = 3 * (\text{last dose date} - \text{first dose date} + 1)$$

[figure not shown]
NOTE: Data entered on **Drug Accountability** CRF page (which only captures details regarding pill count returned) will not be used to calculate and report out subject-level compliance.

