### 5.1. Allocation to Treatment

In this study, at least 360 subjects will be randomized to receive 1 of the regimens described in Table 3. Each dose will consist of 3 tablets (1 tablet from *each of the 3* bottles dispensed).

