**Table 3. Randomized Regimens in Study C1171002**

Regimen	Regimen Description (dosed once-daily)	Number of PF-05221304 tablets				Number of PF-05221304-matching placebo tablets	
		1 mg	5 mg	25 mg	50 mg	1 / 5 mg	25 / 50 mg
A	Placebo	-	-	-	-	2	1
B	PF-05221304 – 2 mg	2	-	-	-	-	1
C	PF-05221304 – 10 mg	-	2	-	-	-	1
D	PF-05221304 – 25 mg	-	-	1	-	2	-
E	PF-05221304 – 50 mg	-	-	-	1	2	-

Allocation of subjects to dosing regimens will occur through the use of an interactive response technology (IRT) system (interactive Web-based response [IWR]). The site personnel (study coordinator or specified designee) will be required to enter or select information including but not limited to the user’s identification (ID) and password, the protocol number, and the subject number. The IRT system will provide a confirmation report containing the subject number, randomization number, and container number(s) assigned. The confirmation report must be stored in the site’s files.

The study-specific IRT reference manual will provide the contact information and further details on the use of the IRT system.

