4 ANALYSIS SETS

Data for all subjects will be assessed to determine if subjects meet the criteria for inclusion in each analysis population set ***close (but prior to)*** database limit-write- access is achieved ***but prior to*** unblinding and releasing the database. Such classifications will be documented per standard operating procedures.

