4.2 Per Protocol Analysis Set

The Per Protocol Analysis Set (PPAS) is a subset of the Full Analysis Set (FAS) excluding the following subjects **for the MMRM analysis on the primary efficacy endpoint:**

- Subjects with compliance, with randomized regimen administered (ie, relevant of the 3 bottles dispensed) over the entire treatment period, of less than 80%.
- Subjects with protocol deviation(s) deemed as compromising primary objective of the study (the list of subjects will be finalized close (but prior to) database limit-write- access is achieved but prior to unblinding and releasing the database).

For the Dose-Response analysis on the primary efficacy endpoint, PPAS is a subset of the FAS excluding the following subjects:

- Subjects with compliance, with randomized regimen administered (ie, relevant of the 3 bottles dispensed) over the entire treatment period, of less than 80%.
- Subjects with protocol deviation(s) deemed as compromising primary objective of the study (the list of subjects will be finalized close (but prior to) database limit-write- access is achieved but prior to unblinding and releasing the database).
- Subjects who withdraw during the randomized treatment period of the trial (post first dose on Day 1 [Visit 5] and before Week 16 [Visit 11]) and/or do not offer MRI (ie, not done or non-evaluable data) at Week 16 [Visit 11].

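### PPAS compliance is scored on active bottles only: this needs treatment information before unblinding, gives placebo subjects no value, and classes the same tablet-taking differently by arm

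*SAP*

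**What the plan says.** SAP Section 4 sets the timing for all analysis sets: "Data for all subjects will be assessed to determine if subjects meet the criteria for inclusion in each analysis population set" shortly before write access to the database is limited, and before unblinding and release. SAP 4.2 repeats the pre-unblinding timing for the list of subjects with disqualifying deviations: "the list of subjects will be finalized close (but prior to) database limit-write- access is achieved but prior to unblinding and releasing the database".

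SAP 4.2 excludes from the PPAS, in both its MMRM and its dose-response definition, "Subjects with compliance, with randomized regimen administered (ie, relevant of the 3 bottles dispensed) over the entire treatment period, of less than 80" percent. Appendix 2.4 says which bottles count: "For PPAS determination, compliance will be calculated using ACTIVE bottles only (ie not using all 3 bottles"). The SAP's table of major changes (item h) also mentions active bottles only, so the choice is deliberate.

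Protocol 5.1 describes dosing: "Each dose will consist of 3 tablets (1 tablet from" each of three bottles). Table 3 gives the contents by regimen. The 2 mg row, for example, reads "PF-05221304 – 2 mg 2 - - - - 1", meaning two active tablets and one placebo tablet of the higher-strength type.

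Protocol 5.3 defines compliance during double-blind treatment differently, as at least 80% in each bottle.

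**The concern.** A compliance rule for a set that is fixed blind should be computable from blinded data. This one is not: nobody can pick out a subject's active bottles without knowing something about that subject's allocation. The SAP does not say who holds that information, or how it is kept from those who decide which deviations compromise the primary objective.

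A second problem remains whatever the blinding arrangement. Placebo subjects have no active bottle, so the criterion has nothing to act on. Among active subjects, the bottles that count change with the dose pair. Compliance exclusions would then act differently by arm in the PPAS, which SAP 6.1.1 labels the sensitivity analysis of the primary endpoint and SAP 6.1.2.2 also uses for the covariate-by-treatment analyses. A difference between FAS and PPAS results could partly reflect the exclusion rule rather than adherence.

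**Working it through.** The plan states no figure on this point to reproduce. The inputs are Protocol Table 3 (bottle contents), Protocol 4.3 (1:1:1:1:1 allocation), Protocol 9.1 (72 per arm, 360 in total) and the 80% limit in SAP 4.2.

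**Step 1. Active bottles by regimen (Table 3).** Lower-strength bottles hold 1 or 5 mg tablets or their placebo; the higher-strength bottle holds 25 or 50 mg tablets or their placebo.

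| Regimen | Lower-strength bottle 1 | Lower-strength bottle 2 | Higher-strength bottle | Active bottles | Planned n |
|---|---|---|---|---|---|
| Placebo | placebo | placebo | placebo | 0 | 72 |
| 2 mg | active | active | placebo | 2 | 72 |
| 10 mg | active | active | placebo | 2 | 72 |
| 25 mg | placebo | placebo | active | 1 | 72 |
| 50 mg | placebo | placebo | active | 1 | 72 |

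**Step 2. What the pattern reveals.** It sorts subjects into placebo (72/360 = 20%), 2 or 10 mg (144/360 = 40%) and 25 or 50 mg (144/360 = 40%). Placebo versus active is revealed for everyone; the exact arm only for placebo. The chance of naming the exact arm rises from 1/5 = 20% to 0.2 × 1 + 0.4 × 1/2 + 0.4 × 1/2 = 60%.

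**Step 3. Same behaviour, different classification.** Active-bottle compliance is taken here as the mean over the active bottles. The order is lower-strength 1, lower-strength 2, higher-strength.

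| Taken from each bottle | Placebo | 2 or 10 mg | 25 or 50 mg | All three pooled | Lowest bottle |
|---|---|---|---|---|---|
| 100%, 100%, 75% | 0/0 | 100%, kept | 75%, excluded | 91.7% | 75% |
| 75%, 75%, 100% | 0/0 | 75%, excluded | 100%, kept | 83.3% | 75% |
| 75%, 100%, 100% | 0/0 | 87.5%, kept | 100%, kept | 91.7% | 75% |

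The last two columns are the same in every arm, so either could be computed blind. In the third row, requiring 80% in each active bottle would exclude the 2 or 10 mg subject. Appendix 2.4 does not say whether two active bottles are pooled. Its formulas are written for three active bottles, with three tablets expected per day; it says they need adapting to this study and gives no adapted version.

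**Step 4. Who is affected.** If all three bottles are at or above 80%, any average of them is too, and the subject is kept in every active arm. If all three are below 80%, the subject is excluded in every active arm. Among active subjects, then, the code can matter only when bottles fall on different sides of 80%. For placebo subjects the rule gives no value at all.

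**The case against.** The strongest reply is that an independent programmer with code access could apply the fixed 80% cut-off and return only a pass/fail flag before the team is unblinded. Nothing in the documents forbids this, so a reader who infers that the timing rule and the active-bottle rule cannot both be met goes too far. What stands is that neither document describes such an arrangement. Protocol 9.5 covers maintaining the blind at interim analyses only, and the procedures cited in SAP 4 concern how classifications are documented. A flag also needs a placebo rule. If placebo is left undefined, the missing flag identifies it; if placebo always passes, every compliance exclusion identifies an active subject.

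A second reply is that the 80% limit is mechanical and judgement enters only through the deviation criterion. That is fair. A reader might infer that those judging deviations will know the arm and select on it, but the documents do not show this. SAP 4.6.2 lists compliance below 80% among the deviations to be reviewed, which makes shared handling possible and no more.

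Third, Protocol 5.2 names only subject and investigator as blinded. This does not settle the matter: SAP 4 itself makes unblinding the deadline, and Protocol 3.3 describes blinded safety review by the sponsor's team.

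Fourth, scoring active drug is a legitimate aim and was chosen on purpose. One could also read the relevant bottles in SAP 4.2 as all three for placebo. Appendix 2.4 does not say so, and its wording points the other way.

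**Conclusion.** The point holds as a gap in blinding and a defect in the definition. As written, the PPAS compliance criterion needs allocation information before unblinding with no stated safeguard, is undefined for placebo, and depends on the arm for active subjects with discordant bottles.

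Its reach is limited. The rule leaves the 72 planned placebo subjects without a value, and can change the class only of active subjects whose bottles straddle 80%. The documents give no count of the latter, and since one tablet is taken from each bottle at every dose it may be small. A reader might take all 360 subjects as misclassifiable, or the exact arm as revealed for all of them. Table 3 supports neither: most classifications may not depend on the code, and four of the five arms are narrowed only to a dose pair.

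The primary FAS analysis, the FAS dose-response model (SAP 6.1.2.1) and the FAS analysis of ALT (SAP 6.2) are unaffected. What suffers is the value of the PPAS as a pre-specified check on the primary result. The conclusion assumes that bottle contents follow Table 3 and that no firewall exists in a document not provided.

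**What to change.** In both PPAS definitions in SAP 4.2 and in Appendix 2.4, define compliance as at least 80% in each of the three bottles, the standard of Protocol 5.3. Compute it from the oral-dosing CRF pages, replace the pooled formulas with one per bottle, and lock the list before unblinding. Report active-bottle compliance descriptively after release. This assumes that the oral-dosing pages record each bottle separately, as the page numbering in the Appendix 2.4 formulas suggests.

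The cost is an SAP amendment to those two sections and the matching programming. The scientific price is that some subjects who took their active drug and missed only placebo tablets leave the PPAS.

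If the sponsor prefers the active-bottle definition, the SAP should name an independent unblinded programmer who returns only a pass/fail flag, and state a placebo rule to the same standard, for example compliance over all three bottles. It should also say whether two active bottles are pooled or judged singly. The flag should not be read beside bottle-level data: in the first example of step 3, a flag of kept or excluded set against 100%, 100% and 75% would itself point to the dose group.
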